9.1.4 Unanticipated Serious Adverse Device Effects

An Unexpected Serious Adverse Device Effect (USADE) is defined as any serious adverse effect on the study subject's health or safety, or any life-threatening problem or death caused by or associated with the device. Also, the effect must not have been previously identified in this Investigational Plan or Instructions for Use in its nature, frequency or severity. USADEs may also include other serious problems associated with the device that affect the rights or welfare of study subjects.

9.2 Adverse Event Documentation

Adverse event information will be collected on all subjects. All adverse events must be reported in the source documents and in the EDC. Adverse events will be evaluated by the investigator and differentiated by:

- Seriousness, as defined in Section 9.1.2
- Severity of the event, defined below.
 - **Mild:** Awareness of signs and symptoms, but easily tolerated; are of minor irritant type, causing no loss of time from normal activities; symptoms would not require medication or a medical evaluation; signs and symptoms are transient.

- **Moderate:** Discomfort severe enough to cause interference with usual activities; requiring treatment, but not extended hospitalization or intensive care for the subject.
- **Severe:** Incapacitating with inability to do work or usual activities; signs and symptoms may be systemic in nature or require medical evaluation and/or treatment; requiring additional hospitalization or intensive care (prolonged hospitalization).
- Relatedness to the device or procedure, defined as:
 - **Unrelated:** AE is due to the underlying disease state or concomitant medication or therapy not related to the study-specific devices or procedures.
 - **Probably not Related:** AE had minimum or no temporal relationship to the study-specific devices or procedures and/or more likely alternative etiology exists.
 - **Possibly Related:** AE had a strong temporal relationship to the study-specific devices or procedures and alternative etiology is equally or less likely compared to the potential relationship to the study-specific devices or procedures.
 - **Probably Related:** AE had a strong temporal relationship to the study-specific devices or procedures and another etiology is unlikely.
 - **Unknown:** Relationship of the AE to the study-specific devices or procedures and alternative etiology is unknown.

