9.1.2 Serious Adverse Events

A Serious adverse event is an adverse event that:

- led to death,
- led to serious deterioration in the health of a subject that
 - resulted in a life-threatening illness or injury,
 - resulted in permanent impairment of a body structure or body function,

- required inpatient hospitalization or prolongation of existing hospitalization,
- resulted in medical or surgical intervention to prevent permanent impairment to a body structure or a body function.
- led to fetal distress, fetal death or a congenital anomaly or birth defect.
- The following clarifications are provided for the serious adverse events:
 - Life-threatening means that the subject was, in the view of the investigator, at immediate risk of death from the event as it occurred. The definition does not include an event that, had it occurred in a more severe form, might have caused death.
 - Hospitalization for elective treatment of a pre-existing condition that did not worsen during the study is not considered a serious adverse event.
 - “Inpatient” hospitalization means the subject has been formally admitted to a hospital for medical reasons. This may or may not be overnight. It does not include presentation at a casualty or emergency room.
 - Important medical events that may not result in death, or be life-threatening, however based upon appropriate medical judgment, may jeopardize the subject and may require medical or surgical intervention to prevent one of the outcomes listed in this definition.
 - Is significant for any other reason.

9.1.3 Anticipated Adverse Events:

Anticipated adverse events are those events that are reasonably expected to occur as a result of the subject’s disease state or treatment. For this study, anticipated adverse events associated with the procedure or post-procedure include, but are not limited to, the following;

- Infections, both deep and superficial
- Allergies or other reaction to device materials
- Temporary or permanent nerve damage as a result of surgery, pressure or hematoma.
- Bruising (hematoma)
- Cardiovascular complications including venous thrombosis, pulmonary embolism, and cardiac arrest.
- Delayed wound healing.

Device-related adverse events are those events that can be directly attributed to the study device and are adjudicated as such by the investigator. These events may include, but are not limited to:

- Infections, both deep and superficial
- Allergies or other reaction to device materials

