- Loosening of the implant as a result of changed condition in load transfer, respectively fatigue wear or tissue reaction to implant or as result of inadequate anchoring technique.
- Dislocation, subluxation or inadequate scope of movement as a result of failure to achieve optimum positioning of the implant.
- Joint stiffness, pain, and swelling
- Bone fractures as a result of one-sided overload or weakened bone structure.
- Temporary or permanent nerve damage as a result of pressure or hematoma.
- Bruising (hematoma) and delayed wound healing.

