10.7 Safety Analysis

All safety endpoints will be summarized separately for investigational and control groups. Similarly, listings with details of the specific complications will be summarized separately as well.

The CCS Component Safety endpoint is any serious, definitely device-related adverse event within 24 Months of surgery. This will be evaluated at the exact two year anniversary (i.e., relative day 730) after the implantation surgery. The safety hypothesis of investigational verses control equality in the likelihood of serious device-related adverse event will be tested using a two-sided Fisher's Exact Test with Type I error rate set to $\alpha=0.05$.

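### The relatedness scale in 9.2 requires strong timing for both related grades, conflicts with the attribution-based definition in 9.1.3, and lets a late implant failure be graded differently from site to site

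*Combined protocol and SAP*

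**What the plan says.** Section 9.2 (Adverse Event Documentation) asks the investigator to grade relatedness to the device or procedure on five levels. The four that matter here are:

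- Probably Related: "AE had a strong temporal relationship to the study-specific devices or procedures and another etiology is unlikely".
- Possibly Related: "AE had a strong temporal relationship to the study-specific devices or procedures and alternative etiology is equally or less likely" (compared with the potential relationship to the device or procedure).
- Probably not Related: "AE had minimum or no temporal relationship to the study-specific devices or procedures and/or more likely alternative etiology exists".
- Unknown: "Relationship of the AE to the study-specific devices or procedures and alternative etiology is unknown".

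The section does not define a temporal relationship and sets no time limit.

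Section 9.1.3 (Anticipated Adverse Events) takes a different approach: "Device-related adverse events are those events that can be directly attributed to the study device and are adjudicated as such by the investigator". Its list of examples includes "Loosening of the implant as a result of changed condition in load transfer, respectively fatigue wear or tissue reaction to implant".

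The classification is used in three places. Item 5 of the CCS component list in section 10 requires no serious device-related complication, which it defines as a severe device-related event. Section 10.7 states: "The CCS Component Safety endpoint is any serious, definitely device-related adverse event within 24 Months of surgery". It continues: "The safety hypothesis of investigational verses control equality in the likelihood of serious device-related adverse event will be tested", by a two-sided Fisher's exact test at 0.05. Section 10.7.2 plans listings of events with a definite relationship to the device and of severe device-related events.

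**The concern.** Strong timing is a natural test of causality for a short exposure. It fits a permanent implant poorly. Loosening, fatigue wear or a tissue reaction may appear 12 to 24 months after surgery, when an investigator may see no close timing to the operation even though no other cause is apparent. Under 9.2 neither related grade can be reached on mechanism alone, and weak timing is enough for Probably not Related. Under 9.1.3 the same event is an example of a device-related event. Nothing says which section governs.

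The test device is a stem-free implant fixed by a hollow screw, and section 5.1 cites 7% aseptic loosening of the humeral head as a known risk, so fixation is a central safety question. If such events are graded inconsistently or downward, the device-related rate may be understated in both arms and the Fisher comparison loses information.

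**Working it through.** **1. The grades side by side (9.2).**

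| Grade | Timing condition | Alternative cause |
|---|---|---|
| Probably Related | strong, required | unlikely |
| Possibly Related | strong, required | equally or less likely |
| Probably not Related | minimal or none is sufficient | or a likelier cause is sufficient |
| Unknown | not applicable | relationship and cause not known |

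**2. A test case.** Take humeral loosening at Month 18 with no other cause identified.

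- If timing is read as closeness to surgery, both related grades are closed and the and/or wording admits Probably not Related.
- If timing is read as continuous exposure to the device, the condition is met, the alternative cause is unlikely, and the event is Probably Related.
- Under 9.1.3, timing does not enter and the event is a listed device-related example.

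The text permits both grades for identical facts.

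**3. The link to the endpoints.** Section 10.7 requires a definite relationship and 10.7.2 lists on the same term, but the scale in 9.2 stops at Probably Related. CCS item 5 says severe device-related, without naming a grade. No section states which grades of 9.2 count. Whichever related grades are counted, both carry the timing condition.

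**4. What counts without the grade.** In the CCS, any reoperation, removal or modification is a failure. So are excess humeral or glenoid radiolucency, migration, disassembly and device fracture at Month 24. Only the periprosthetic fracture criterion mentions device-relatedness. Section 10.6 compares device survival by log-rank with no relatedness condition stated, and 10.7.2 lists all adverse events in the ITT cohort. Two gaps remain. The film criteria do not cover dislocation or subluxation, and they accept radiolucency above 2 mm in up to 3 of 9 Eclipse zones or 5 of 15 control zones.

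**5. Group sizes for the illustration.** Section 10.4 gives 98 and 196. Check: control n = (1.645 + 0.842)² × 0.88 × 0.12 × (1 + 1/2) / 0.10² = 97.9, so 98, and 2 × 98 = 196. Inflation: 98/0.85 rounds up to 116 and 196/0.85 to 231, total 347. The plan's figures reproduce and the point does not alter them.

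**6. Fisher power, by exact enumeration (two-sided 0.05).** The documents give no expected rate of serious device-related events, so the rates and the share lost are assumptions. A share s lost multiplies both rates by (1 − s); for example, 10% v 2% with half lost becomes 5% v 1%.

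| Assumed true rates | Controls | None lost | 25% lost | 50% lost |
|---|---|---|---|---|
| 10% v 2% | 98 | 75% | 58% | 32% |
| 10% v 2% | 77 | 66% | 48% | 21% |
| 7% v 2% | 98 | 39% | 25% | 10% |
| 7% v 2% | 77 | 32% | 18% | 4% |
| 5% v 2% | 98 | 15% | 9% | 2% |

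The 77-control rows reflect section 3.1, which allows control randomization to stop at that number. The 25% column corresponds, for example, to half of the events being mechanical and half of those being graded out (0.5 × 0.5 = 0.25).

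**The case against.** The best reply is that 9.2 asks about a relationship to devices or procedures, so exposure to an implant is continuous and a late failure can meet the timing condition. On that reading the alternative-cause limb still separates the grades, and 9.1.3 points investigators towards it. This stands as a possible reading. It is not stated, however, and the opposite reading is equally open, which is the source of the inconsistency. The Unknown grade does not help for recognised loosening with no other apparent cause, and it is not a related grade. The medical monitor evaluates all serious adverse events (9.3), but no authority to change a grade is stated.

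A reader might infer that late failures necessarily fall under Probably not Related and drop out of the safety endpoint. The documents do not support that: there is no time limit that excludes them, and no rule ties the grades of 9.2 to the endpoint.

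A reader might also infer a material bias towards non-inferiority. The non-inferiority test is on the CCS, where the components in step 4 catch many such failures whatever their grade. The Fisher test is a test of equality.

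It is also fair to say that the power figures could mislead. Device-related events in 9.1.3 include infection, nerve damage and hematoma, many of them perioperative, so the share lost is probably well below the share of late mechanical failures that are misgraded. At 5% v 2% the Fisher test has only 15% power even with perfect grading.

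**Conclusion.** The point holds as a conflict between 9.2 and 9.1.3 that leaves the grading of late implant failures to each site's reading of an undefined term. It can understate events in CCS item 5, the Fisher test in 10.7 and the device-related listings in 10.7.2. The effect on the primary CCS is limited to events that miss its reoperation, radiographic and Constant score components, such as a late dislocation managed without reoperation and with an adequate score.

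The documents allow no estimate of how many events would be misgraded. The power losses (75% to 58% or 32% at 10% v 2%) show sensitivity under assumed rates and loss shares; they do not predict what will happen. The wording should be corrected because the change is cheap and the conflict concerns a safety classification.

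**What to change.** 1. In 9.2, let both related grades be met by a temporal relationship or by a plausible device mechanism regardless of time since implantation, keeping the existing alternative-cause limbs.
2. Require a more likely alternative etiology for Probably not Related, so that weak timing alone no longer suffices. This brings 9.2 into line with 9.1.3.
3. State which grades of 9.2 count as device-related in CCS item 5, 10.7 and 10.7.2, and either add a definite grade or remove that term. Without this step, rewording the scale does not settle what enters the endpoint.
4. Apply the revised wording to loosening, dislocation or subluxation, disassembly and fracture events already recorded. Investigators know which device they implanted, so the re-grade should be done blind to arm where feasible.

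The cost is wording in 9.2, section 10 and the adverse event form guidance, some re-grading work, and a device-related rate that may look slightly less favourable in both arms.

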9.3 Adverse Event and Unanticipated Adverse Device Effect Reporting

At every subject encounter, the investigator will determine if there has been an adverse event since the last encounter.

For this study, serious adverse events must be reported immediately (within 24 hours) directly to ArthroX, Inc. by completing the Adverse Event form and entering it into EDC. At the time of the initial report, the outcome (resolution status) may not be known. Updated information must be entered into EDC until final resolution of the event.

Unanticipated Serious Adverse Device Effects must also be reported by the investigator to the approving IRB as soon as possible, but not later than 10 working days after the investigator first learns of the effect. The sponsor must report to the FDA, all reviewing IRBs and participating investigators within 10 working days of notification from the investigator of a USADE.

The medical monitor will provide medical surveillance on adverse events and will evaluate all Serious Adverse Events (SAEs).

9.4 Device Complications

For this study all device complication including; damaged parts, cracked parts, packaging –device component missing, packaging-broken in package, piece broke from device, frozen or other will be collected and reported in EDC.

9.5 Safety Monitoring

As the study sponsor of this clinical study, Arthrex Inc. will be responsible to monitor it for safety. In the circumstance where unanticipated adverse device event or serious adverse events occur due to a procedure, Arthrex, Inc., will convene a review committee which will determine any unreasonable risk to subjects, or if the study should be reviewed for modification or early termination.

10 Statistical Method and Sample Size Calculation

10.1 Definition of Month 24 Composite Clinical Success (CCS)

A literature search was conducted to estimate expected post-operative Constant scores and subjective success rate of TSA procedures. Fifteen (15) articles were found [1-15]. Four (4) articles were excluded due to data that appeared to be from the same data base and may contain the same subjects. The 11 included articles contained data on a total of 1095 subjects. All 11 of the articles contained post-operative Constant Scores, and 6 contained standard deviation associated with the post-operative Constant Score. Four (4) of the articles contained age/sex Adjusted Constant Scores and 3 out of those 4 contained standard deviation associated with the age/sex adjusted Constant Score. Four (4) of the 11 articles contained subjective satisfaction scores. The entire compilation can be seen in Appendix 2-12. Weighted averages based on sample size were calculated for Constant Scores, standard deviations, and percent satisfied using the compiled literature. The data is summarized in Table 1.

Table 1: Summarized weighted averages

Constant Score	66.2 ± 16.2
Adjusted Constant Score	87.6 ± 22.8
% Good/Satisfied or Better	93%
# of Subjects	1095

The data suggest that 93% of subjects were satisfied or better with the outcomes of TSA. Any pass/fail criterion for minimum acceptable Constant Score should produce an over-all success rate for non-investigation devices similar to those reported in literature (93%). To estimate the range of Constant Scores that would include 93% of the subjects, an 86% prediction interval was calculated. The results of the prediction interval can be seen in Table 2, and the calculation is illustrated in

Figure 1.

Table 2: Calculated prediction interval

	86% PI	Minimum Score
Constant Score	23.9	42.3
Adjusted Constant Score	33.7	53.9

Based on the literature available, a minimum Adjusted Constant score of 53.9 (or ≥ 54) should produce a pass rate of approximately 93%.

[figure not shown]

Figure 1: Adjusted constant score distribution plot

10.2 Determining the Adjusted Constant Score for Inclusion Criteria:

A literature search was conducted to estimate the expected Pre-operative Constant scores for Inclusion Criteria. To our knowledge there is no definitive statement regarding the use of pre-operative Constant Score as an inclusion/exclusion criterion; however, the range of expected pre-operative Constant scores can be derived. Fifteen (15) articles were found [1-15]. Of those, 4 were excluded due to data that appeared to be from the same data base and may contain the same subjects [1, 12, 13, and 14]. Ten (10) of the remaining eleven (11) articles contained pre-operative Constant Scores, and of those ten, three (3) reported standard deviation. Four (4) of the articles contained age/sex Adjusted Constant Scores and 3 out of those 4 contained standard deviation associated with the age/sex adjusted Constant Score. The entire compilation can be seen in the Appendix 2-13. Weighted averages based on sample size were calculated for Constant Scores and standard deviations using the compiled literature. The data is summarized in Table 3.

Table 3: Summarized weighted averages

Constant Score	28.2 ± 11.7 (n = 752)
Adjusted Constant Score	37.3 ± 15.6 (n = 619)

A 95% prediction interval suggests 95% of the subjects enrolled had pre-operative Adjusted Constant Scores between 6.6 and 67.9. A conservative Adjusted Constant Score of ≤ 50 for Inclusion Criteria was chosen to eliminate the possibility of biases.

The goal of the study is to determine non-inferiority of the Eclipse™ Shoulder Prosthesis compared to the Arthrocare's Univers™ II Shoulder Prosthesis. Non-inferiority will be evaluated by the 2 year Composite Clinical Success (CCS) and is based on:

1. Adjusted Constant score change ≥ 10 . This is based off the minimum clinically relevant difference (Brorson S, 2009) (Haahr JP, 2005) (Pfahler M, 2006)
2. Adjusted Constant Score ≥ 54 . This is based on ~~the above~~ calculations in Table 2.
3. Radiographic Outcomes Success: Patient meets acceptance criteria for humeral radiolucency, humeral migration/subsidence, glenoid radiolucency, glenoid migration/subsidence device condition, and periprosthetic fracture.

Investigational Group (Eclipse)

Radiolucency will be evaluated in each of nine Zones from the Neutral Rotation AP and Axillary views.

- **Acceptance Criterion:** Radiolucency > 2 mm in ≤ 3 zones (out of 9 zones)
- **Rationale:** The methods used are based off the 3/8 ratio presented by Sperling as a risk for implant loosening. With nine zones for the investigational humeral implant, $3/8$ of 9 = 3.375. As such, radiolucency in 3 zones falls below the criterion for radiolucency established by Sperling, and, as such is the acceptable amount of radiolucency for this device (Sperling JW, 2000).

Control Group

Radiolucency will be evaluated in each of the 15 Zones adapted from Sperling et al. for the humeral component of the *control* device from the Neutral Rotation AP and Axillary views (Sperling JW, 2000).

- **Acceptance Criterion:** Radiolucency > 2 mm in ≤ 5 zones (out of 15 zones)
- **Rationale:** The methods used are based off the 3/8 ratio presented by Sperling as a risk for implant loosening. With nine zones for the investigational humeral implant, $3/8$ of 15 = 5.625. As such, radiolucency in 5 zones falls below the criterion for radiolucency

established by Sperling, and, as such is the acceptable amount of radiolucency for this device (Sperling JW, 2000).

Humeral Migration/Subsidence

Humeral Migration/Subsidence will be graded as ‘Absent’ or ‘present’

- **Absent:** Humeral component displacement ≤ 3 mm relative to the baseline time point
- **Present:** Humeral component displacement > 3 mm relative to the baseline time point

Humeral Migration/Subsidence Endpoints will be assessed for change relative to month 3 image.

Success Criterion for Humeral Migration: Absent Humeral Migration/Subsidence

Glenoid Radiolucency

Glenoid Radiolucency (Keel & Pegged) will be graded as described per the method of Lazarus et al. (2002). As the geometry of the pegged and keeled components is different, Lazarus developed and validated a grading schema that would provide a means to compare the two different designs of glenoid components.

Keel Glenoid Component

Grade 0: No radiolucency

Grade 1: Radiolucency at superior and/or inferior flange

Grade 2: Incomplete radiolucency at keel

Grade 3: Complete radiolucency (≤ 2 mm around keel)

Grade 4: Complete radiolucency (> 2 mm around keel)

Grade 5: Gross loosening

Pegged Glenoid Component

Grade 0: No radiolucency

Grade 1: Incomplete radiolucency around one or two pegs

Grade 2: Complete radiolucency (≤ 2 mm wide) around one peg only, with or without incomplete radiolucency around one other peg

Grade 3: Complete radiolucency (≤ 2 mm wide) around 2 or more pegs

Grade 4: Complete radiolucency (> 2 mm wide) around 2 or more pegs

Grade 5: Gross loosening

Success Criterion for Glenoid Radiolucency: Grade ≤ 3 glenoid Radiolucency

- **Rationale:** Previously, researchers have utilized a glenoid lucency of ≥ 4 (per criteria of Lazarus 2002) to determine those patients “at risk” for device malfunction due to glenoid lucency as 24 Months post-op. Haines et al. (2006) observed, in a prospective clinical trial of shoulder arthroplasties (n=124 shoulders, n=113 patients), 14% of patients at > 24 Months had a glenoid lucency score ≥ 4 (per criteria of Lazarus 2002). These patients, having what the authors describe as “at risk” implants, demonstrated a 78% survival rate at seven years, but only a 46% survival rate at ten years, compared to a survival rate of 84% at 10 years for the entire patient cohort. (Haines et al. 2006)

Glenoid Migration/Subsidence

Glenoid Migration/Subsidence will be graded as ‘Absent’ or ‘Present’

- **Absent:** Glenoid component displacement ≤ 3 mm relative to the baseline time point
- **Present:** Glenoid component displacement > 3 mm relative to the baseline time point

Glenoid Migration/Subsidence Endpoints will be assessed for change relative to month 3 image.

Success Criterion for Glenoid Migration: Absent Glenoid Migration/Subsidence**Device Condition**

Device Condition will be evaluated to assess the condition and integrity of the device. Device Condition will be graded as ‘Intact’, ‘Disassembly’ or ‘Fracture’ in accordance with the following definitions:

- **Intact:** No evidence of fractured or disassembled hardware. The hardware is intact.
- **Disassembly:** Presence of device component disassembly
- **Fracture:** Presence of fracture or breakage of one or more device components

Success Criterion for Device Condition: Intact device condition**Periprosthetic Fracture**

Periprosthetic fracture will be graded as ‘Absent’, ‘Present – Humeral’ in accordance with the following definitions:

- **Absent:** No evidence of periprosthetic fracture(s) about the humeral or glenoid components

- **Present – Humeral:** Presence of periprosthetic fracture(s) about the humeral component that is not present on the relative baseline time point

Success Criterion for Periprosthetic Fracture: Absence of device-related Periprosthetic fracture

4. No reoperation, removal, or modification of any study component up to the subject's completion of the study
5. Lack of serious device related complications (defined as a severe device-related adverse event) up to the subject's completion of the study.

Per the World Health Organization Definition of adverse events, a Grade 3 (or severe) adverse event significantly limits the patient's ability to perform routine activities despite symptomatic therapy.

